5.1 Trial design

The ZosterFluCov trial is a multicentre, parallel-group placebo-controlled RCT in which participants, laboratory staff analysing samples, and clinicians assessing causality will be blinded to the treatment.

5.2 Key design features to minimise bias

Selection/allocation bias will be prevented by concealed randomisation. The allocation will not be revealed until sufficient information to uniquely identify the participant has been entered into the allocation database.

Performance and detection bias will be minimised by blinding participants and clinicians assessing causality to the vaccine received. Laboratory staff analysing samples will be blinded. Laboratory staff who are processing samples only do not need to be blinded. We will also define procedures for follow-up and monitor adherence to the protocol. The participant information leaflet (PIL) and the process of obtaining informed consent will describe the uncertainty about the effects of giving the two vaccines together compared to separately. Therefore, in the event

of inadvertent unblinding of a participant, he or she should not have a strong expectation that one should be better than the other.

Attrition bias will be minimised by using established methods developed in the Coordinating Centre to maximise the quality and completeness of the data (e.g., regular monitoring of data, querying of data in the trial database). Instances of non-adherence will be fully documented and reviewed at trial meetings and an action plan for maximising compliance drawn up as appropriate. Data will be analysed by intention to treat (i.e., according to the treatment allocation, irrespective of future management and events), and every effort will be made to include all randomised patients.

Reporting bias will be minimised by pre-specifying trial outcomes and following a detailed analysis plan which will be prepared in advance of any comparative analyses of the trial data.

5.3 Setting

Participating clinical trial sites that include NHS hospitals and primary care sites.

5.4 Trial population

Healthy adults aged 50 and over or those with established medical co-morbidities with stable symptoms on the day of randomisation and without prior history of shingles vaccination in the last 5 years. Prespecified maximum recruitment limits will be set for the following age groups; 69 and under and 70 and over to ensure that we have adequate representation of older adults for whom HZV is currently recommended. Recruitment of those from the global majority (Black, Asian and non-Caucasian groups) is particularly encouraged. Both men and women will be encouraged to participate.

5.4.1 Inclusion criteria

1. Participants who, in the opinion of the investigator, can and will comply with the requirements of the protocol.
2. Written informed consent obtained from the participant prior to any study-specific procedure.
3. Adults aged 50 and over at the time of randomisation.
4. Participants must have documented history (e.g. NHS app, GP record) of receiving their initial course (usually two doses) of any type of COVID-19 vaccination, irrespective of the type of COVID-19 vaccine received.
5. Female participants of childbearing potential must be willing to ensure that they or their partner use effective contraception from 1 month prior to first vaccination continuously until 3 months after final vaccination*.

** A woman of childbearing potential is defined as a pre-menopausal female who is capable of becoming pregnant. Menopause can be diagnosed in a woman aged over 50 after one year of amenorrhoea (this applies only if the woman is not using hormonal contraception).*

Acceptable forms of contraception for volunteers of female sex include:

- *Established use of oral, injected or implanted hormonal methods of contraception*
- *Placement of an intrauterine device (IUD) or intrauterine system (IUS)*
- *Total hysterectomy*
- *Bilateral Tubal Occlusion*
- *Barrier methods of contraception (condom or occlusive cap with spermicide)*
- *Male sterilisation, if the vasectomised partner is the sole partner for the subject*
- *True abstinence, when this is in line with the preferred and usual lifestyle of the subject (Periodic abstinence and withdrawal are not acceptable methods of contraception)*

5.4.2 Exclusion criteria

1. Any clinical condition that in the opinion of the investigator might pose additional risk to the participant due to participation in the study.
2. History of reaction or hypersensitivity likely to be exacerbated by any component of the study intervention including allergic reaction to any component of any of the study vaccines, known reactions related to study vaccines e.g. history of myocarditis, Guillain-Barre Syndrome.
3. Unstable medical condition on the day of enrolment as determined by clinical history and examination.
4. Bleeding disorders or continuous use of anticoagulation medicine, such as coumarins and related anticoagulants (i.e., warfarin) or novel oral anticoagulants (i.e. apixaban, rivaroxaban, dabigatran and edoxaban). Use of aspirin is allowed.
5. Any confirmed or suspected immunosuppressive, or immunodeficient condition, based on medical history and physical examination. People living with HIV that is well controlled can be included in the study.* Those with a new diagnosis or an AIDs defining illness in the past 12 months cannot be included.
6. Use of immunosuppressive medication, ongoing, long term or planned, defined as more than 14 days in total of immunosuppressant treatments. For corticosteroids this will mean more than 14 days of prednisolone >20mg/day or equivalent. Use of inhaled, intra-articular and topical steroids is allowed.
7. Use or planned use of long-acting immune modifying drugs in the 12-month period before randomisation (e.g. infliximab).
8. COVID-19 or influenza vaccination 90 days prior to the study vaccination
9. Previous vaccination with a live herpes zoster vaccine within the past 5 years.

10. Administration of monoclonal antibodies (including those targeting SARS CoV2), immunoglobulins and/or blood products during the 3 months before the first dose of the study vaccines, up to 1 month after the last dose or planned during the study period.

11. Planning to or concurrently participating in another interventional clinical study.

12. Pregnancy, lactation or willingness/intention to become pregnant within the study period.

**Defined as less than 50 copies/ml (convert as needed from IU/ml) on the last two occasions >3 months apart, and a CD4 over 500 when last checked.*

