SMPC	Summary of Medicinal Product Characteristics
SUSAR	Suspected unexpected serious adverse reaction - an untoward medical occurrence suspected to be related to a medicinal product that is not consistent with the applicable product information and is serious.
TMF	Trial master file
TMG	Trial management group
TSC	Trial steering committee
VRR	Vaccine response rate
UHBW	University Hospitals Bristol and Weston NHS Foundation Trust
UKCRC	UK Clinical Research Collaboration
WHO	World Health Organisation

1. Trial Synopsis

Herpes zoster (HZ) is a vaccine preventable infection with an associated mortality of up to 7%.¹ In the UK vaccination against HZ is recommended for adults on their 70th birthday.² Uptake of HZ vaccine (HZV) is suboptimal therefore strategies to improve uptake are needed. Routine reporting of HZV uptake suggests that uptake is greater during influenza vaccination season.³ It is assumed that increased uptake at this time is due to opportunistic vaccination with HZV when patients attend for influenza vaccination. A recombinant herpes zoster vaccine with adjuvant (RZV) has been recommended in the UK since 2021. Up until May 2023 concomitant administration of RZV with either adjuvanted flu vaccine or COVID-19 vaccine (C-19) was not recommended due to concern about misattribution of side-effects and limited experience with COVID-19 vaccines. The policy was updated in May 2023 to allow co-administration of COVID-19 vaccines with any vaccine. This was based on recent evidence supporting the acceptable safety profile of a COVID-19 vaccine with RZV and to improve timely protection and uptake.⁴ There is still a need however for safety data with co-administration of second dose of RZV as the adverse event profile differs between the doses and there is a lack of published data on the safety and immunogenicity of RZV and adjuvanted flu vaccine.

Figure 1 shows trial schema.

Table 1 Trial synopsis

Trial title	A phase IV, multi-centre, randomised controlled trial to assess immunogenicity and safety of COVID-19 and seasonal influenza vaccine given to healthy adults or those with underlying medical conditions when co-administered with a recombinant herpes zoster vaccine with adjuvant
Internal ref (or short title)	ZosterFluCov

Trial registration	ISRCTN26495549
Sponsor	University Hospitals Bristol and Weston NHS Foundation Trust Research & Innovation Department [name]
Funder	GSK
Clinical Phase	Phase IV

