4.1 Primary outcome

Part A: Assessment of co-administration of COVID-19 and RZV

Co-Primary Endpoints

1) Immunogenicity of C19

Anti-S protein Ig concentrations expressed as Geometric Mean Concentrations (GMCs) for both strains in C19 vaccine/RZV (first or second dose, groups 2 & 3) and C19 vaccine alone (group 1), will be used to calculate between group ratios expressed a geometric mean ratio (GMR), at 1 month after vaccination with C19 vaccine.

2) Immunogenicity of RZV

Anti-gE Ig concentrations expressed as GMCs after co-administration of C19 vaccine/RZV (first or second dose) and RZV alone, 1 month after 2nd dose of RZV, and between-group ratios expressed as GMRs.

Success criteria:

Part A of the trial will be classified as a success if both of the following meet the success criteria:

- 1) The combined administration of C19 vaccine and RZV (first or second dose) will be considered non-inferior to C19 vaccine alone if the lower limit of the 95% confidence interval for the (GMR) of anti-S protein Ig concentrations exceeds 0.67, the standard WHO non-inferiority margin for recommendation of new vaccines.⁷, AND

2) The combined administration of C19 vaccine and RZV (first or second dose) will be considered non-inferior to RZV alone if the lower limit of the 95% confidence interval for the GMR of Anti-gE Ig concentrations exceeds 0.67.

3) Safety of RZV

The rate of grade 3 and 4 solicited systemic adverse reactions (Table 2) after C19 vaccine/RZV (first or second dose, groups 2 and 3) and RZV alone 7 days after vaccination (groups 1-5) This is a descriptive outcome.

Table 2 Solicited AEs collected on post vaccination diary cards

Systemic solicited AEs
Fatigue
Fever
GI symptoms†
Headache
Myalgia
Shivering

†Gastrointestinal symptoms include nausea, vomiting, diarrhoea and/or abdominal pain

Note: The above AEs are assumed to be related and will be classed as adverse reactions.

Part B: Assessment of co-administration of adjuvanted influenza vaccine and RZV

Co-Primary Endpoints

1) Immunogenicity of aQIV

HAI titres expressed as GMCs in aQIV/RZV (first or second dose, groups 4 & 5) and aQIV alone (group 3) will be used to calculate between group ratios, expressed as GMR at one month after aQIV vaccination.

2) Immunogenicity of RZV

Anti-gE Ig concentrations expressed as GMCs after co-administration of aQIV/RZV (first or second dose) and RZV alone, 1 month after 2nd dose of RZV, and between-group ratios expressed as GMRs.

Success criteria:

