5.8 Research procedures: participants

Participants will be required to do, or undergo, the following tasks or investigations specifically for the trial which are also outlined in schedule of events (Table 4).

Table 4 Schedule of events

Visit	V1	V2	V3	V4	V5	V6
Timing (days)	D0	D28	D56	D84	D112	D140
Window periods (days)	-	D26-32	D56-60	D82-86	D112-116	D140-146
Eligibility	x					
Urine sample*	x		x		x	

Randomisation	x					
Vaccinations	x		x		X	X**
Bloods (serum) (COVID-19 subset)	x	x	x	x		
Bloods (serum) (Influenza subset)	x	x	x	x		
Bloods (serum) Anti-gE Ig	x		x	x		x
Blood (whole) RZV Cell- mediated immunology (CMI)	x		x	x		x
Blood (whole) exploratory immunity	x	x				
+Diary Card training	x					
Diary Card review						
Safety Review						
Quality of life survey	x		X***		X***	
Missed workdays			x		x	

* Urinary pregnancy testing for female participants of child-bearing potential only**Group 1 will receive the flu vaccine at visit 6 if in the winter vaccination season.

***Quality of life survey completed 7 days after vaccination

Volunteers interested in participating will be asked to complete an ‘expression of interest/initial screening’ questionnaire available via a public website. See section 12.3 for details of how the public will be made aware of the trial.

The ‘expression of interest/initial screening’ questionnaire will assess whether the volunteer meets the key inclusion criteria for participation (e.g. age, received their initial course (usually two doses) of COVID-19 vaccinations). If these criteria are met, they will be asked to indicate their electronic consent to proceed to more detailed screening, and for the research team to contact their GP for further clarification of medical history (if required) and confirmation of vaccination record.

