13.1 Sample size calculation

Sample size calculations have been performed to test all primary immunogenicity objectives in both part A and part B of the trial. All sample size calculations were performed using the SSI module in Stata.⁹

Part A: Assessment of co-administration of COVID-19 vaccine and RZV

We hypothesise that (1) immunogenicity (anti-S protein Ig concentrations, both Original and Omicron strains) of concomitant administration of C19 and RZV (first or second dose) will be non-inferior to C19 alone, and (2) immunogenicity (anti-gE Ig concentrations) of concomitant administration of RZV (first or second dose) and C19 will be non-inferior to RZV alone.

The power calculations to test hypotheses in part A are provided in Table 10.

Table 10 Sample size estimates for part A

Outcome	Sample size excluding 10% inflation for dropout	SD (log10 scale)	Assumed true GMR	Non-inferiority margin (log10 scale)	Power for each outcome	Conjunctive power for part A
Anti-S Ig	95	0.35	1	0.174	92.9%	80.1%
Anti-gE Ig	95	0.35	1	0.174	92.9%	

A sample size of 106 per group will provide 80% power to test all part A hypotheses using a 2.5% one-sided significance level and allowing for 10% dropout.

Part B: Assessment of co-administration of adjuvanted influenza vaccine and RZV

We hypothesise that (1) immunogenicity (for 3 of the strains included in the vaccine; HAI influenza A H3N2, HAI influenza A H1N1 and HAI influenza B Victoria) of concomitant administration of aQIV and RZV (first or second dose) will be non-inferior to aQIV alone, and (2) immunogenicity (anti-gE Ig concentrations) of concomitant administration of RZV (first or second dose) and aQIV will be non-inferior to RZV alone.

The power calculations to test hypotheses in part B are presented in Table 11.

Table 11 Sample size estimates for part B

Outcome	Sample size excluding 10% inflation for dropout	SD (log10 scale)	Assumed true GMR	Non-inferiority margin (log10 scale)	Power for each outcome	Conjunctive power for correlated outcomes (HAI)*	Conjunctive power for part B
HAI influenza A H3N2	216	0.45	1	0.174	98.0%		
HAI influenza A H1N1	216	0.54	1	0.174	91.8%	80.7%	80.6%
HAI influenza B Victoria	216	0.57	1	0.174	88.7%		
Anti-gE Ig	216	0.35	1	0.174	99.93%	-	

* Estimated using correlation matrix from ComFluCOV HAI data; conjunctive power for HAI outcomes was calculated using R.

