A sample size of 240 per group will provide 80% power to test all part B hypotheses using a 2.5% one-sided significance level and allowing for 10% dropout.

Final sample size justification

A sample size of 960 (120 into groups 1 and 2, 240 into groups 3-5, after inflating to fit a 1:1:2:2:2 allocation ratio) will allow us to adequately assess all primary immunogenicity objectives.

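### Section 5.4 rules out any shingles vaccine in the last 5 years but exclusion criterion 9 rules out only live vaccine, so a site using the numbered list could enrol a recent RZV recipient

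*Protocol*

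**What the plan says.** Two places in the protocol set a rule on earlier zoster vaccination.

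- Section 5.4 (Trial population), which opens the eligibility section, takes adults "without prior history of shingles vaccination in the last 5 years". It does not distinguish live from recombinant vaccine.
- Section 5.4.2, criterion 9, excludes "Previous vaccination with a live herpes zoster vaccine within the past 5 years". It does not mention recombinant vaccine.

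No inclusion criterion in 5.4.1 and no other exclusion addresses earlier RZV. Criterion 8 sets a 90-day rule for the other two trial vaccines, COVID-19 and influenza, so RZV is the only trial vaccine with no numbered rule on prior receipt. Section 5.8 gives "age, received their initial course (usually two doses) of COVID-19 vaccinations" as its examples of what the first questionnaire checks. Sections 5.8 and 5.8.1 provide for confirming vaccination records before the full eligibility check, but state no zoster rule.

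The synopsis shows that such recipients can exist: "A recombinant herpes zoster vaccine with adjuvant (RZV) has been recommended in the UK since 2021".

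The endpoint at stake is in section 4.1. For part A it is "Anti-gE Ig concentrations expressed as GMCs after co-administration of C19 vaccine/RZV (first or second dose) and RZV alone, 1 month after 2nd dose of RZV". Part B has the matching endpoint with aQIV. In both parts success requires that the "lower limit of the 95% confidence interval for the GMR of Anti-gE Ig concentrations exceeds 0.67".

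**The concern.** Someone given RZV in 2021 or later, and so within 5 years of a protocol whose version 5.0 is dated November 2023, fails the population statement but passes the numbered list. The protocol does not say which text governs, and about 15 sites could read it differently.

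Two consequences follow directly if such a person is enrolled. First, the anti-gE co-primary is meant to describe the response to a two-dose RZV course. In a prior recipient, the sample one month after the second trial dose reflects three or more doses. Second, section 4.2 reports grade 3 and 4 reactions separately for first and second doses, and the synopsis justifies the trial partly because reactions differ between doses. A prior recipient's next dose would be tabulated as a first dose.

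A third consequence needs an assumption. If earlier RZV reduces any interference from co-administration, mixing primed and naive participants moves the geometric mean ratio (GMR) towards 1. In a non-inferiority comparison that direction favours success.

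**Working it through.** **The two rules side by side**

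| Vaccine received in the last 5 years | Section 5.4 | Criteria in 5.4.1 and 5.4.2 |
|---|---|---|
| Live zoster vaccine | not in population | excluded (criterion 9) |
| Recombinant vaccine (RZV) | not in population | no criterion applies |

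Only the second row conflicts. Neither text covers RZV given more than 5 years ago.

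**The protocol's own power figures.** Inputs from section 13.1, Tables 10 and 11: SD 0.35 (log10), margin 0.174, true GMR 1, one-sided 2.5%. Power = Φ(0.174/SE − 1.96), with SE = 0.35 × √(1/n₁ + 1/n₂).

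- Part A, 95 per group: SE = 0.0508, power 92.9% (stated 92.9%).
- Part B, 216 per group: SE = 0.0337, power 99.93% (stated 99.93%).

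Both reproduce, and the eligibility conflict does not alter them.

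**Illustration of dilution.** Assumptions not in the documents: a share f of each arm is primed, primed participants have GMR 1, and naive participants have GMR exactly 0.67 (log10 = −0.1739).

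- Pooled log10 GMR: δ = (1 − f) × (−0.1739). For f = 5%, δ = −0.1652, GMR 0.684. For f = 10%, δ = −0.1565, GMR 0.697.
- Chance of declaring anti-gE non-inferior: Φ((δ + 0.174)/SE − 1.96).

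The layouts are the two in the protocol's tables, plus 108 v 108 and 216 v 108. Those are the planned groups of 120 and 240 less 10% dropout, with group 1 as comparator; in Table 3 it alone receives both RZV doses without another active vaccine.

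| Evaluable per arm | SE | f = 0 | f = 2% | f = 5% | f = 10% |
|---|---|---|---|---|---|
| 95 v 95 | 0.0508 | 2.5% | 2.9% | 3.7% | 5.3% |
| 108 v 108 | 0.0476 | 2.5% | 3.0% | 3.8% | 5.6% |
| 216 v 108 | 0.0412 | 2.5% | 3.0% | 4.0% | 6.2% |
| 216 v 216 | 0.0337 | 2.5% | 3.2% | 4.5% | 7.5% |

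The shift depends on the product of f and the fraction of interference removed. So 10% primed with half the interference gives the same result as 5% primed with none.

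**Possible added variance.** If primed participants also sat 0.3 log10 higher (assumed, and not removed by baseline adjustment), the SD becomes √(0.35² + f(1 − f) × 0.3²). That is 0.356 at 5% and 0.361 at 10%. Part A anti-gE power would fall from 92.9% to 92.0% and 91.3%.

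**The case against.** The strongest reply is that 5.4 heads the whole eligibility section. Read as governing, it already bars these people and nobody enters wrongly. That stands as far as it goes: the documents show two rules in conflict, not a decision to admit prior RZV recipients. It does not resolve the conflict, because the numbered list is the detailed statement of eligibility and is the narrower of the two.

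A reader might infer that primed participants start high, respond little, show a ratio near 1 and fail the 4-fold response definition in section 4.2. The protocol says nothing about the anti-gE response to revaccination, so none of this can be asserted. A reader might also take the coverage of 48.2% to 76.7% quoted in section 2 as the share at risk. That figure does not separate live from recombinant vaccine, and recipients of live vaccine within 5 years are already excluded. Routine vaccination is at age 70 while the trial enrols from 50, which points to a limited pool.

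The error rates concern one endpoint. Part A also needs anti-S non-inferiority and part B needs three HAI strains, so the chance of a false success for a whole part is lower.

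The design gives some protection. Randomisation is stratified by centre, so uneven reading by sites should not unbalance the arms. The model in section 13.4 adjusts for baseline, and Figure 1 shows anti-gE sampled before the first RZV dose in every group, which can absorb some added variance. Neither feature undoes dilution of the ratio.

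**Conclusion.** The contradiction stands and is more than clerical. Followed as written, the numbered criteria admit people whose anti-gE result is not the response to a two-dose course and whose first trial dose is not a first dose. That much needs no assumption beyond such a person being enrolled.

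The effect on the non-inferiority test is conditional. With 5-10% primed, no interference in them and a naive GMR exactly at the margin, the single-endpoint error is about 4-6% instead of 2.5%, reaching 7.5% at 216 per group. At 2% primed it is about 3%. Zero interference in primed participants is the extreme case for dilution towards 1, and the documents give neither the share nor the response. The figures show direction and plausible scale; they do not estimate this trial's error rate. The documents do not support a claim that prior recipients have entered or that the error is inflated in fact.

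**What to change.** Reconcile sections 5.4 and 5.4.2 into one rule that names the vaccines and the period. The simplest way is to align criterion 9 with the sponsor's own statement in 5.4: any zoster vaccine, live or recombinant, within the stated 5 years. The sponsor should confirm at the same time that this period is the one intended for recombinant vaccine.

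Add the zoster check to the confirmation of vaccination status already carried out at pre-screening (sections 5.8 and 5.8.1).

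For anyone already enrolled after earlier RZV, record it, keep them in the intention-to-treat analysis, and add a sensitivity analysis of anti-gE without them. The protocol names no per-protocol set, so this should be specified as a sensitivity analysis.

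Cost: a one-line eligibility amendment, one more item at pre-screening and a small loss of eligible volunteers. The sample size does not change.
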